7 STUDY INTERVENTION DISCONTINUATION AND PARTICIPANT DISCONTINUATION/WITHDRAWAL

7.1 DISCONTINUATION OF STUDY INTERVENTION

Providers should exercise clinical judgment and can at their discretion disregard any information the CDS offers. As such, patients will receive usual dental care, regardless of study arm.

Hospitalizations documented within the HealthPartners electronic health record that occur within a 72-hour window following the index extraction encounter will be chart reviewed for severity and relatedness on a quarterly basis during the intervention period by Co-investigator and/or PI [name]. These hospitalizations rates will be compared at a frequency determined by the DSMB or quarterly whichever is greater.

Based on the relevant data, the study team in consultation with the DSMB would determine whether the study intervention needed to be modified or discontinued.

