8.2 SAFETY AND OTHER ASSESSMENTS

The study does not include objectives or endpoints concerning safety. However, the monitoring activities described below will be conducted to assess possible harm.

Identify whether the CDS inappropriately fires or inappropriately offers considerations

Data source: Provider report to alert study team about potential issues or concerns

Procedures:

1. Providers randomized to an intervention arm will be offered training.

2. They will be instructed to notify the study team when clinical judgement differs from the CDS
3. Notification options: (a) Contact Co-Investigator [name] or PI [name]; (b) select a "feedback" button contained within the CDS

Identify potential adverse events

Data source: HealthPartners electronic health record

Procedures:

1. Gather hospitalizations, emergency department visits, observational bed, and subsequent opioid prescribing made within 3 days post-extraction procedure

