9.2 SAMPLE SIZE DETERMINATION

- Primary Efficacy Endpoint(s):

H1 (alternative): Providers in the CDS and CDS-E strategy arms will reduce their likelihood of prescribing opioids for patients following extractions more than providers in the SP arm.

H1 patient-level endpoint: A binary code (0/1) indicating that a provider prescribed an opioid medication to the patient on the date of the index extraction encounter.

Sample size and power: Preliminary data from 2018 indicates there will be 6,900 unique patients age 16 and higher with a permanent tooth extracted by 51 dental providers in the baseline period and also an estimated 6,900 unique patients age 16 and higher with a permanent tooth extracted by 51 dental providers during the intervention period. The study analysis is expected to have at least

this many patients. Fully 40% of encounters in the baseline period with patients having a permanent tooth extraction included a prescription for opioid use, and the provider-level opioid use $ICC=0.3$. Assuming the use of a generalized linear mixed model, with $\alpha=0.05$, two-sided tests, the planned analysis for H1 can detect a differential raw reduction of 23% from pre- to post-intervention opioid prescribing when comparing CDS or CDS-E patients (40% with opioid prescriptions pre-implementation to 15% post-implementation) to SP patients (40% with opioid prescriptions pre-implementation to 38% post-implementation) with 80% power. Power calculations were conducted with PASS v11 (NCSS Software).

- Secondary Efficacy Endpoint(s):

H2 (alternative): Providers in the CDS and CDS-E strategy arms will increase their likelihood of recommending NSAIDs and/or APAP at the extraction encounter and not prescribing opioids for patients following extractions more than providers in the SP arm.

H2 endpoint: A binary code (0/1) indicating that a provider both 1) prescribed or recommended in the treatment plan use of non-opioid analgesics and 2) did not prescribe an opioid prescription on the date of the extraction encounter.

Sample size: This analysis will use the same analytic sample described for H1. The rate is unknown but will be lower than the percentage not prescribing opioids in H1 (60%) since the endpoint is a composite requiring no opioid prescription and also recommendation of non-opioid analgesic.

H3 (alternative): Patients will report higher levels of the extent of shared decision making in the CDS-E arm than the CDS or SP arms.

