9.3 POPULATIONS FOR ANALYSES

Patient Encounter Study Population for H1, H2

The analytic denominator for H1 and H2 will consist of up to 16,800 (8400 baseline and 8400 intervention) first extraction encounters of patients aged 16 and higher and linked to a study-eligible provider, and who have a permanent tooth extraction during the year prior or year after the implementation of the strategies.

Patient Study Population for H3, H4

The analytic denominator for H3 and H4 will start with the approximately 8,400 patients who meet the criteria for the analytic denominator during the intervention period for H1 and H2 above. This analytic dataset will be further reduced to the approximately 1,520 patients who are approached to complete and complete a patient survey within 6 days of the index encounter. Of the approximately 1,520 patients approached it is expected that the analysis for H3 and H4 will include data from 1,200 patients.

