9.4.4 SAFETY ANALYSES

The study does not include objectives or formal endpoints concerning safety. However, potential harm monitoring activities will be conducted as described in section 8.2, and analysis activities conducted as described below.

Identify whether the CDS inappropriately fires or inappropriately offers considerations

The frequency of notifications and content areas (usability, potential safety, or other) will be summarized by study arm (CDE or CDS-E) and provider type.

Identify potential adverse events

Frequencies, proportions and 95% confidence intervals on proportions of patients having hospitalizations documented in the HealthPartners electronic health record within 72-hours of the extraction encounter deemed as adverse events will be summarized by study arm. The

patient encounter study population for H1 and H2 for patients seen following the implementation of the interventions will be used for this analysis. Events with non-overlapping confidence intervals on the proportions by study arm will prompt the study team to assess diagnostic codes related to the encounters from the electronic health record. Frequencies and proportions of diagnostic codes by study arm will be computed.

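### The planned hospitalization review and arm comparison cover only each patient's first extraction, although the interventions also operate at later extractions

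*Combined protocol and SAP*

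**What the plan says.** Section 9.4.4 plans frequencies, proportions and 95% confidence intervals for patients with hospitalizations "within 72-hours of the extraction encounter deemed as adverse events will be summarized by study arm". For the denominator it states that the "patient encounter study population for H1 and H2 for patients seen following the implementation of the interventions will be used for this analysis". Section 9.3 defines that population as "first extraction encounters of patients aged 16 and higher and linked to a study-eligible provider".

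Section 7.1 is the only other place that plans a comparison of hospitalization rates. It covers hospitalizations "that occur within a 72-hour window following the index extraction encounter will be chart reviewed for severity and relatedness", on a quarterly basis. Section 6.3 defines the index encounter as the initial extraction visit in the intervention period at which the study criteria are met.

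The data collection step in 8.2 is worded more broadly: "Gather hospitalizations, emergency department visits, observational bed, and subsequent opioid prescribing made within 3 days post-extraction procedure". Section 8.3.4 repeats this, and neither section mentions a first-extraction limit. Section 6.3 adds that data from index and subsequent encounters of eligible patients are stored.

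**The concern.** One encounter per patient suits H1 and H2, whose sample size is counted in unique patients. The plan carries the same restriction into harm monitoring without giving a reason.

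Exposure does not stop at the first visit. Section 6.1.1 describes decision support for patients who receive extractions, and handouts in CDS-E, with no first-visit limit. Section 6.3 has the CDS web service running at each encounter. The possible harms named in 2.3.1, including under-controlled pain and erroneous therapy leading to adverse events, could follow any exposed extraction.

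As written, a hospitalization two days after a patient's second exposed extraction is neither scheduled for the 7.1 chart review nor counted in the 9.4.4 comparison. Section 7.1 makes such data part of the basis for deciding, with the DSMB, whether the intervention is modified or discontinued. Of the EHR events listed in 8.2, hospitalization is the only one that 9.4.4 compares by arm.

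**Working it through.** **Tracing the population.** The plan states no figure for this point, so the check starts with the cross-references.

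| Section | Role | Encounters covered |
|---|---|---|
| 9.4.4 | Arm comparison of hospitalizations | H1/H2 population, after implementation |
| 9.3 | Defines the H1/H2 population | First extraction encounters |
| 7.1 | Chart review and rate comparison | Index extraction encounter |
| 6.3 | Defines index; describes storage | Index is the initial visit; index and subsequent data stored |
| 8.2, 8.3.4 | Harm data collection | Within 3 days after an extraction procedure, no first-only limit |

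Section 9.4.4 speaks of the extraction encounter rather than the index encounter, but the population it names holds at most one intervention-period encounter per patient. The 9.3 total agrees with its parts: 8,400 + 8,400 = 16,800. No section adds later extractions to an arm comparison.

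**Scale.** Section 9.2 expects "6,900 unique patients age 16 and higher with a permanent tooth extracted by 51 dental providers during the intervention period", so an even split gives 6,900/3 = 2,300 patients per arm. The 9.3 maximum gives 8,400/3 = 2,800. Let x be the mean number of later extraction encounters per patient in the intervention period. The documents do not give x; the range below is assumed. The share of extraction encounters outside the comparison is x/(1+x). If encounters were independent and equally risky, including them would multiply interval width by about 1/sqrt(1+x).

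| x (assumed) | Later encounters per arm, 2,300 patients | Same, 2,800 patients | Share left out | Narrowing if independent |
|---|---|---|---|---|
| 0.02 | 46 | 56 | 2.0% | 1.0% |
| 0.05 | 115 | 140 | 4.8% | 2.4% |
| 0.10 | 230 | 280 | 9.1% | 4.7% |
| 0.20 | 460 | 560 | 16.7% | 8.7% |
| 0.30 | 690 | 840 | 23.1% | 12.3% |

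**Clustering.** The last column is an upper bound, because encounters cluster within patients and within providers. For provider clustering alone, the variance is proportional to [1 + (n − 1)ρ]/n per provider. Take n = 6,900/51 = 135.3, an assumed event ICC of ρ = 0.01, and x = 0.20:

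- first encounters only: [1 + 134.3 × 0.01]/135.3 = 0.01732
- all encounters, n = 135.3 × 1.2 = 162.4: [1 + 161.4 × 0.01]/162.4 = 0.01610
- width ratio: sqrt(0.01610/0.01732) = 0.964, a narrowing of 3.6% rather than 8.7%

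Correlation within patients would reduce this further.

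**The existing trigger.** Section 9.4.4 acts on non-overlapping intervals. With exact 95% intervals (my assumption, as the plan names no method), 2,300 patients per arm and no events in one arm, another arm needs 9 events before the intervals separate. Against 1 event it needs 12. Events left out make an already insensitive trigger slower to fire.

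**The case against.** The strongest defence is that one encounter per patient is a coherent choice. Sections 7.1, 9.3 and 9.4.4 all use it, and 9.4.4 reports proportions of patients. Returning for another extraction happens after exposure and may be influenced by it. A later extraction may also be done by a provider in another arm, since 4.2 notes that providers float across clinics. First encounters avoid both problems. This stands, and it is why later extractions belong in a supplementary summary rather than a replacement.

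The evidence that later events are already collected is also less than conclusive. Section 8.1 uses the same extraction-procedure wording for the H1 data pull, which is analysed at the index encounter only. The subsequent encounters in 6.3 could be follow-up visits. The texts permit the wider reading but do not prove it.

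A reader might infer more than the documents support:

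- **That these events are never examined.** SAE reporting in 8.3.6 is not limited to the index extraction, and 8.3.2 counts inpatient hospitalization as serious. The DSMB reviews safety data by arm under a charter (10.1.6) that is not among the documents. The gap is in the systematic review and the written comparison.
- **That hospitalization is the only harm compared by arm.** H4 compares patient-reported pain across arms, and 8.3.3.3 lists inadequately managed pain as an expected adverse event. Section 9.4.4 also summarizes CDS notifications by intervention arm.
- **That patients with repeated extractions are excluded.** They enter through their first extraction; only their later encounters are outside.

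**Conclusion.** The restriction is real. As written, the 7.1 review and the 9.4.4 comparison omit hospitalizations within 72 hours of a later exposed extraction. Under the assumed 0.02 to 0.30 later extractions per patient, that is about 2% to 23% of intervention-period extraction encounters, and the same share of events if risk per encounter is equal. The true share cannot be derived from the documents, which give neither a repeat-extraction rate nor a hospitalization rate.

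The gain in precision would be modest, below the 1% to 12% that independence implies. The main benefit is fuller capture of rare events under exposure. The protocol sets no safety objectives or formal safety endpoints (8.2, 9.4.4), so this is an inexpensive improvement rather than a defect that undermines the trial. It does not justify replacing the first-encounter population.

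**What to change.** Keep the first-encounter summary in 9.4.4 and the first-encounter population for H1 and H2. Then:

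1. In 7.1, extend the chart review to hospitalizations within 72 hours of any intervention-period permanent-tooth extraction by a study provider in an eligible patient.
2. In 9.4.4, add a supplementary per-encounter summary of these hospitalizations by arm, with arm assigned by the provider performing that extraction.
3. Use intervals that allow for clustering by patient and by provider.
4. State in 8.2 and 8.3.4 whether collection covers every extraction or only the index one.

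If first-only monitoring is intended, 7.1 and 9.4.4 should say so and give the reason.

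The cost is some additional chart review. No new collection is needed if the EHR pull already covers later extractions, as 8.2 permits; otherwise the pull must be widened. Patients whose extractions fall in different arms will contribute to more than one arm, and the report should give their number.

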4 STUDY DESIGN

4.1 OVERALL DESIGN

This study is a prospective, 3-arm, cluster randomized trial (Phase III) in which up to 60 dental providers (accrual goal: n=51) practicing at HealthPartners dental clinics are randomized in a 1:1:1 allocation ratio to either standard practice (SP) or one of two clinical decision support arms (CDS or CDS-E). Patients (up to n=8,400, accrual goal: n=6,900) are exposed to the study arm of their dental provider. Opioid prescribing measured at the patient-level serves as the primary outcome. Opioid prescribing data for patients (up to n=8,400, goal: n=6,900) seen in the baseline period and unexposed to the intervention is utilized in the analysis to examine secular trends in opioid prescribing. Additional outcomes are also measured at the patient-level include: a recommendation or prescription for non-opioid analgesics from the electronic health record and patient reported outcomes about shared decision making and pain identified through surveys.

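### The only numeric between-arm harm criterion in 9.4.4, non-overlap of separate 95% intervals, is far less sensitive than a direct comparison of arms

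*Combined protocol and SAP*

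**What the plan says.** Section 9.4.4 opens by stating that "The study does not include objectives or formal endpoints concerning safety". It then plans a harm summary by arm: "Frequencies, proportions and 95% confidence intervals on proportions of patients having hospitalizations documented in the HealthPartners electronic health record within 72-hours" of the extraction, limited to those judged to be adverse events. The denominator is the "patient encounter study population for H1 and H2 for patients seen following the implementation of the interventions will be used for this analysis". The action rule follows: "Events with non-overlapping confidence intervals on the proportions by study arm will prompt the study team to assess diagnostic codes". Frequencies of those codes are then tabulated by arm.

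The section gives no expected rate, interval method, pairing of arms, treatment of provider clustering or schedule for the rule.

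Other sections also look at harm. Section 7.1 has 72-hour hospitalizations chart reviewed each quarter for severity and relatedness, and adds: "These hospitalizations rates will be compared at a frequency determined by the DSMB or quarterly whichever is greater". The study team, consulting the DSMB, then decides whether to modify or stop the intervention. Section 10.1.6 has the DSMB assess safety data for each arm at least twice a year. Neither section states a threshold.

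**The concern.** Checking whether two separate 95% intervals overlap is often taken as equivalent to a 5% test of the difference. It is much stricter. Section 9.4.1 tests the efficacy contrasts at a two-sided 0.05, so the harm screen demands stronger evidence than the efficacy analysis. Yet all it triggers is a tabulation of diagnosis codes, where a false alarm costs little and a missed excess costs more.

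The harms this trial foresees are hard to see chart by chart. Section 2.3.1 names under-controlled pain as a possible consequence of the shift in prescribing, and 8.3.3.3 classes inadequately managed pain, drug interactions and analgesic side effects as expected events. An excess of expected events shows mainly in a comparison of arms. If the one comparison with a stated criterion rarely reacts, overlapping intervals could be read as reassurance that the data do not give.

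**Working it through.** **Plan's own figure.** The documents state no operating characteristic for this rule, so there is none to reproduce. The 80% power in 9.2 concerns opioid prescribing and does not bear on it.

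**Inputs from the documents.** Section 4.1: "Patients (up to n=8,400, accrual goal: n=6,900) are exposed to the study arm of their dental provider", with providers "randomized in a 1:1:1 allocation ratio". Per arm this is 6,900/3 = 2,300 at the goal and 8,400/3 = 2,800 at the maximum. The interval level is 95% (9.4.4).

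**Assumptions.** SP 72-hour rate of 0.1% to 1%; a true doubling under CDS; equal arms; independent patients (no provider clustering).

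**Step 1: nominal level of non-overlap.** With equal standard errors s, the intervals separate when the difference exceeds 1.96 × 2s. The standard error of the difference is √2 × s, so the rule needs z > 1.96 × 2/√2 = 2.77. The two-sided level is 2 × (1 − Φ(2.77)) = 0.0056, about one ninth of 0.05.

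**Step 2: a concrete count.** Take 5 hospitalizations among 2,300 SP patients.
- Clopper-Pearson: the SP upper limit is 0.507%. CDS needs 20 events (lower limit 0.532%).
- Wilson: the SP upper limit is 0.508%. CDS needs 19 events (lower limit 0.529%).
- Direct comparison by pooled score statistic, z > 1.645: 12 events suffice. The difference is 7/2,300 = 0.00304, the pooled rate is 17/4,600 = 0.00370, the standard error is √(0.00370 × 0.99630 × 2/2,300) = 0.00179, and z = 1.70. With 11 events, z = 1.50.

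The rule therefore needs close to a four-fold observed excess at this count.

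**Step 3: chance of a prompt if the CDS rate is truly doubled.** Binomial probabilities are summed over all pairs of counts, n = 2,300 per arm. The direct rule is a lower 90% score bound for the difference above 0, which for equal arms is the pooled z > 1.645. The Fisher column is a one-sided 5% exact test.

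| SP rate | Expected events, SP / CDS | Non-overlap, Clopper-Pearson | Non-overlap, Wilson | Direct, 90% score | Direct, Fisher |
|---|---|---|---|---|---|
| 0.1% | 2.3 / 4.6 | 0.5% | 1.2% | 21% | 11% |
| 0.2% | 4.6 / 9.2 | 3.0% | 4.7% | 34% | 25% |
| 0.5% | 11.5 / 23 | 16% | 20% | 63% | 57% |
| 1% | 23 / 46 | 47% | 51% | 88% | 86% |

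**Step 4: sensitivity of the result.**
- At 2,800 per arm, non-overlap (Clopper-Pearson / Wilson) gives 1.0% / 1.8%, 4.5% / 6.6%, 23% / 27% and 59% / 63% at the same four rates.
- Wald intervals at 2,300 give about 8% at both 0.1% and 0.2%.
- If any of the three arm pairs counts and both CDS arms are doubled, Clopper-Pearson gives 1%, 6%, 26% and 64%.
- At an SP rate of 2%, non-overlap fires about 88-89% of the time, so the weakness is confined to low rates.
- Allowing for provider clustering would widen the per-arm intervals and lower the non-overlap figures. It would lower the direct figures too.

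**Step 5: false prompts with no true difference.** Over these rates, non-overlap fires in the CDS-above-SP direction 0.01% to 0.3% of the time, and the 90% score rule about 5% per contrast per look. For two contrasts at four cumulative quarterly looks (575 per arm per quarter, even accrual assumed), simulation gives 15% to 19% for at least one false prompt.

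**The case against.** The strongest reply is that this rule controls little. Every documented 72-hour hospitalization is chart reviewed quarterly without any interval condition, rates are compared at least quarterly, and the DSMB sees safety data by arm. Non-overlap gates only an added tabulation of codes. That stands, and it rules out several stronger readings that a reader might infer:

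- *That the rule is the only arm-level harm safeguard.* It is not. It is the only numeric between-arm criterion in this document. The DSMB charter and the Data Safety Monitoring Plan may contain others, and neither was available.
- *That the rule governs the quarterly comparisons.* Section 7.1 mentions neither intervals nor overlap, and 9.4.4 gives no schedule. Joining the two is inference.
- *That modifying or stopping the intervention, or a conclusion of no harm, hangs on overlap.* Section 7.1 refers to the relevant data in general. No text makes overlap decisive or commits the trial to concluding that there is no harm.
- *That a doubling would almost never be flagged.* That needs an SP rate of about 0.2% or lower. A low rate is plausible for an outpatient procedure, and counting only events judged adverse lowers it further, but the documents give none.

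It is also fair to say that a better rule cannot create events. At 0.1% the direct score rule still misses a doubling about 79% of the time, and an exact method misses more.

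None of this defends non-overlap itself. The unconditional reviews carry no numeric criterion, so they do not make good an insensitive one, and the direct rule is markedly more sensitive at every rate from 0.1% to 1%.

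**Conclusion.** The point holds in a limited form. The one stated numeric between-arm harm criterion works at about a two-sided 0.006 level for equal arms, and more strictly for rare counts. For a true doubling with 2,300 per arm, it prompts the code review about 0.5-1%, 3-5%, 16-20% and 47-51% of the time at SP rates of 0.1%, 0.2%, 0.5% and 1%, against about 21%, 34%, 63% and 88% for a lower 90% score bound.

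These probabilities rest on an assumed rate, a doubling chosen for illustration, equal arms and no clustering. The ordering of the two rules is the same at each of the four rates; the absolute figures depend on the rate. The defect affects one follow-up step in harm monitoring. It does not touch the efficacy analyses or remove the reviews in 7.1 and 10.1.6. It should still be changed, because the gain in sensitivity is large and the cost small.

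**What to change.** In 9.4.4, replace the non-overlap rule as follows:

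- For CDS minus SP and for CDS-E minus SP, report the difference in proportions with a 90% score-type interval. Name the method, and allow for provider clustering where counts permit.
- Prompt the diagnostic-code review for a contrast when the lower bound exceeds 0.
- Keep the per-arm proportions and 95% intervals as description only.
- State when the rule is applied, and whether the quarterly comparison in 7.1 uses it.

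The cost is protocol and SAP wording, plus about a 5% chance per contrast per look of a code tabulation that finds nothing. That accumulates if the rule is applied repeatedly, to roughly 15-19% over two contrasts and four quarterly looks under the assumptions above. The report should also say that sensitivity stays limited when events are very rare, so that absence of a prompt is not read as evidence of no harm.
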